Clinical Trial Protocol Synopsis

Protocol title : The impact of soiled airway management on CPR quality
Objectives : To evaluate the influence of soiled airway management on the quality of CPR
Background : Regurgitation is an adverse event common during cardiopulmonary resuscitation (CPR) and occurs in 20%-32% of patients experiencing out-of-hospital cardiac arrest (OHCA). It can impair ventilation, induce aspiration, and decrease survival to hospital discharge. Gastric fluid in the airway obscures the laryngeal view, thereby considerably decreasing the first-pass success of endotracheal intubation (ETI) by paramedics. A human cadaver study reported that ETI outperforms other airway management devices, such as the i-gel, laryngeal mask, and laryngeal tube, in preventing aspiration when regurgitation occurs during CPR. However, ETI is also associated with multiple and prolonged CPR pauses. Compared with the use of supraglottic airway (SGA) devices, ETI results in more hands-off time during CPR. Recent randomised clinical trials have revealed that airway management with an SGA device provides superior outcomes to those of ETI in patients with OHCA. However, ETI remains the preferred management strategy for an airway affected by regurgitation in patients with OHCA. Current guidelines focus on the quality of CPR because it is a key determinant of survival in patients with OHCA. However, evidence regarding the impact of regurgitation during ETI on CPR quality is limited. This manikin simulation study assessed CPR quality during ETI in airways with and without regurgitation.
Study Design : A prospective compare study

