Each CPR-intubation sequence comprised two segments: a compression segment and a hands-off segment. Presents the rules for determining the start and end of a CPR-intubation sequence. CCF was defined as the proportion of time spent on chest compression in each CPR-intubation sequence. The longest interruption time was defined as the longest hands-off duration in each sequence. An intubation attempt was defined as the insertion of the laryngoscope blade into the mouth and its subsequent withdrawal from the mouth. Intubation time was defined as the period between the start and the end of an intubation attempt. The time spent checking the endotracheal tube position by manual ventilation through the endotracheal tube was not included in the CPR-intubation sequence.

Two video cameras were setup to record the entire simulation process. Two observers reviewed the video records independently to identify the start and end of each CPR-intubation sequence, any intubation attempts, and the hands-off and compression segments of each sequence. Disagreements were resolved by reaching mutual consensus. The HQCPR application on an Android device recorded chest compression depth, rate, and interruptions (defined as no chest compression [hands off] for >1 s). The data from both the video recording and the HQCPR application were used in subsequent analysis. Continuous data are presented as medians with interquartile ranges, and categorical data are presented as frequency counts and percentages. The continuous data were compared using the Wilcoxon rank sum test in the first CPR-intubation sequence and the Mann-Whitney U test in the second and third sequences. The McNemar test was used to compare the intubation success rate in the first sequence, and Pearson's chi-square test was used for the second and third sequences. The continuous data from all three CPR-intubation sequences were compared using the Kruskal-Wallis test. Post hoc analysis was performed using Conover's test.

The association of CPR quality metrics with successful intubation was evaluated using a Cox proportional hazards regression model. The results of multivariate analyses are presented as hazard ratios (HRs) with corresponding 95% confidence intervals (CIs). A two-tailed $P < 0.05$ indicates statistical significance. MedCalc Statistical Software version 19.2. (MedCalc Software, Ostend, Belgium) was used for data analysis.

Effect :

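### If the Cox model for intubation success runs on elapsed time, whole-sequence CCF and longest interruption entered as fixed covariates bias its hazard ratios

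*Protocol*

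**What the plan says.** Everything relevant is in the Protocol's Methods, with one supporting remark in the Background. The statistical paragraph names the model: "The association of CPR quality metrics with successful intubation was evaluated using a Cox proportional hazards regression model". It then says: "The results of multivariate analyses are presented as hazard ratios (HRs) with corresponding 95% confidence intervals (CIs". The CPR quality metrics are the four primary outcomes: CCF, compression depth, compression rate and longest interruption.

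Two of these are summaries of a complete sequence: "CCF was defined as the proportion of time spent on chest compression in each CPR-intubation sequence" and "The longest interruption time was defined as the longest hands-off duration in each sequence".

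The durations that the Protocol defines are elapsed ones: "Intubation time was defined as the period between the start and the end of an intubation attempt". On the end of the sequence it adds: "The time spent checking the endotracheal tube position by manual ventilation through the endotracheal tube was not included in the CPR-intubation sequence". The video observers were asked "to identify the start and end of each CPR-intubation sequence, any intubation attempts, and the hands-off and compression segments of each sequence".

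For the Cox model, the Protocol gives no time origin, time axis, unit of analysis or updating of covariates. The rules for where a sequence starts and ends seem to sit in a figure or table that is not reproduced. Whether the five 30:2 cycles before the first attempt count in the sequence is therefore unknown here.

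**The concern.** At each event time, a Cox model compares the covariates of those still at risk. This is valid only if the covariates are known by that time. CCF and longest interruption become known when the sequence ends, which is also when the outcome is decided. If the clock measures elapsed time, the covariates partly encode how long the clock ran. Longest interruption has a further problem of its own: the longest pause so far can only grow as a sequence goes on.

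At stake is the interpretation of the reported HRs. An HR below 1 for longest interruption would read as pauses lowering the chance of intubation. An HR below 1 for CCF would read as better compression continuity hindering intubation. Either could appear with no such relation present.

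**Working it through.** The Protocol gives no event count, expected HR or sample-size calculation for this model, so there is no figure to reproduce.

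**Inputs from the Protocol.** There are 54 EMT-Ps, and each takes every role in both scenarios, giving 54 × 2 = 108 first sequences. A sequence consists of compression time plus hands-off time. Tests are two-sided at 0.05.

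**Assumptions.** Mean attempt 30 s, success 75% or 80%, and pauses generated independently of success and of attempt length, so that no true association exists.

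**Step 1, the identity.** Let T be sequence length, H total hands-off time and L the longest interruption. CCF = (T − H)/T, so T = H/(1 − CCF). Since H ≥ L, T ≥ L/(1 − CCF), with equality when there is only one pause.

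- One 10 s pause: CCF 0.80 gives T = 10/0.20 = 50 s; CCF 0.90 gives T = 10/0.10 = 100 s.
- Pauses of 10 s and 6 s: CCF 0.80 gives T = 16/0.20 = 80 s (bound 50 s); CCF 0.90 gives T = 16/0.10 = 160 s (bound 100 s).

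At a fixed L, a higher CCF goes with a later end. At a fixed CCF, a longer L does too. A later end means a lower apparent hazard. Several pauses per sequence are to be expected, since the Background notes: "However, ETI is also associated with multiple and prolonged CPR pauses". L is then only a proxy for H, and the reconstruction of T is partial.

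**Step 2, both metrics entered together, fixed, on elapsed time (null data, 108 sequences).**

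| Setting | HR per +0.1 CCF | Significant | HR per +1 s longest interruption | Significant |
|---|---|---|---|---|
| Attempt only, random pauses, 0.6–2.2 per sequence; adjusted for depth, rate and scenario | 0.40–0.61 | 98–100% | 0.49–0.74 | 100% |
| Attempt only, six other pause patterns; the two metrics alone | 0.11–0.60 | 99–100% | 0.41–0.77 | 100% |
| Five cycles counted, 5.6–6.3 pauses per sequence; adjusted as in row 1 | 0.27–0.49 | 49–96% | 0.74–0.79 | 70–99.8% |

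Two further settings with the five cycles counted show that the CCF result is not stable. About 1.5 pauses beyond the cycles gave a CCF HR of 0.72 with 18% rejection. Frequent short pauses gave 1.12 with 5% rejection.

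The first and third rows were also varied to 54 sequences, 50–95% success and a mean attempt of 20–50 s. Rejection for CCF and longest interruption was then 78–100% and 91–100% (attempt only), or 11–76% and 26–82% (five cycles counted).

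**Step 3, one metric at a time.**

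- Longest interruption, adjusted for scenario: HR 0.78–0.92, rejection 41–99.7% in the base case and 20–100% over all variations.
- Longest interruption in the six other patterns: 0.87–0.94 in five of them (62–100%). It was 0.99 (4%) with a fixed pause at the start, which cannot grow with follow-up.
- CCF: 0.67–1.09 in the random-pause settings and 0.53–1.35 in the six patterns. The direction is not determined.

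**Step 4, what is not affected.** Depth and rate gave HRs of 0.97–1.03. With sequence number as the time axis, the HRs for both metrics were 0.99–1.00, with rejection of about 1% or less. If failed attempts last 1.6 times longer, that axis gave 0.92–0.96 with 0.5–4% rejection.

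**Step 5, repairs on null data.**

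- Clock from blade insertion, both metrics computed only up to time t: HRs 0.98–1.02, rejection 3.7–8.0%. Time-updating in the six other patterns gave 0.98–1.04, with rejection of 2–11% in 100 runs each.
- Metrics from the five pre-intubation cycles as fixed covariates: HRs 0.99–1.02 for longest interruption and 0.99–1.14 for CCF, rejection 4.3–7.8%.
- Clock moved to blade insertion, whole-sequence metrics kept fixed (five cycles counted): HRs 0.24–0.46 for CCF and 0.76–0.85 for longest interruption, rejection 43–99.8%. This does not repair the problem.

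**The case against.** The Protocol gives the Cox model two sentences. The time axis, covariate list and covariate handling could properly sit in a statistical analysis plan that is not at hand. Sequence number is a possible axis: the other comparisons are organised by first, second and third sequence, and failure is defined partly by three unsuccessful attempts. On that axis there is essentially no artefact. The word multivariate could also mean each metric adjusted for scenario, without the two metrics sharing a model. All the simulated durations are assumed, and the association is neither the stated objective nor a listed outcome.

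Much of this stands. The point has to be conditional, the sizes illustrative, and the statement about CCF weaker than that about longest interruption. What does not fall is the core. The Protocol itself fixes the whole-sequence definitions and pairs them with a time-to-event model, and the only durations it defines or collects are elapsed ones. Followed on its natural reading, the text conditions on covariates that are known only when follow-up ends. That is a fault in the stated method, not merely an omitted detail.

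**Conclusion.** The concern holds conditionally. If the axis is elapsed time and the two metrics are fixed covariates, the HRs are biased with no true association. For longest interruption the bias is below 1 in nearly all settings tested, whether it is entered alone or jointly. For CCF it is usually below 1 under joint entry with longest interruption, but the direction depends on the pause pattern and on whether the five cycles count; CCF alone can move either way. False-positive rates near 100% apply to attempt-only sequences with joint entry and are much lower in some other settings.

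A reader might infer more than this:

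- That the plan definitely uses fixed covariates on elapsed time. It does not say so; both conditions are inferred from its definitions.
- That both HRs must fall below 1. The joint CCF HR of 1.12 in one setting rules that out.
- That the simulated ranges bound the effect. They reflect chosen attempt lengths, success rates and pause patterns.
- That the trial's main results are compromised. The primary between-scenario comparisons do not use this model.

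The point should be settled before the HRs are interpreted. Confidence is medium, because the time axis is unstated.

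**What to change.** State the Cox time axis. If it is sequence number, a sentence saying so removes most of the concern.

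If it is elapsed time, start the clock at blade insertion. Enter CCF and longest interruption as time-dependent covariates, using only compressions and pauses up to time t. The segment timings read from video supply what is needed. The cost is a sentence or two of analysis text, recoding into start-stop records, and possibly software other than MedCalc. No new data are required.

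For first sequences only, metrics from the five pre-intubation cycles could serve as fixed covariates instead. This answers a narrower question than CPR quality during intubation. It is not available for second and third sequences, because only two BVM ventilations precede a reattempt.

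Under either option, allow for each EMT-P contributing sequences in both scenarios, for example with standard errors clustered by EMT-P. The simulations treated sequences as independent and did not test this part.
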